7.3. Statistical Analyses

Data for each group (Cognitively Normal, MCI, Parkinson) will be analyzed separately. However the same analytic approach will be taken for each, as described below. Some analyses will be truncated for the MCI groups due to the smaller sample size.

Aim 1: Aim1 will test the hypothesis that individuals in the active stimulation group will show improved cognitive function compared to the sham group. Separate mixed model ANOVAs (2 [Group: Active Stimulation, Sham stimulation] x 2 [Occasion: Pre-testing, Post-testing]) will be conducted using the executive and Memory outcome variables. When significant, appropriate post-hoc analyses will be conducted. Additional analytic techniques will involve 'change score' analyses, as well as analyses examining predictors of changes (i.e., age, education, gender).

Aim 2: Aim 2 will test the hypothesis that individuals in the active stimulation group will show improved emotion/psychological function compared to the sham group. Separate mixed model ANOVAs (2 [Group: Active Stimulation, Sham stimulation] x 2 [Occasion: Pre-testing, Post-testing]) will be conducted using the mood outcome variables (mood modules NIH Toolbox, STAI, POMS, BDI-II). When significant, appropriate post-hoc analyses will be conducted. Additional analytic techniques will involve 'change score' analyses, as well as analyses examining predictors of changes (i.e., age, education, gender).

Aim 3: This neuroimaging aim is exploratory and will test the hypothesis NIR intervention will produce pre-post increases in frontal and temporal brain markers of MRS ATP function and pre-post increases in connectivity in frontal and medial temporal lobe mediated resting state brain networks (resting state fMRI). Although this aim will require extensive data reduction, the overall data analytic plan is similar to that of Aims 1 and 2.

Aim 4: This is aim is specific to Parkinson disease and will test the hypothesis that active NIR stimulation will result in greater pre-post intervention improvement in motor parameters (UPDRS, fine motor speed, gait, balance) than sham. Separate mixed model ANOVA's will be conducted similar to those described in Aims 1 and 2.

Finally, we plan to examine whether various 'factors' might potentially be moderators or mediators to intervention success. WE plan to examine age, education, gender, health comorbidities, processing speed and mood.

8. Methodological Limitations

Only two previous human studies have conducted sham controlled trials. Thus, there is a potential impact of placebo in producing positive effects on cognition. The current study attempts to control for this. Another issue pertains to the penetrance of near infrared light through the skull. Most transcranial NIR light applied to the human cranium penetrates 1 cm into the tissue, reaching cortical tissue but not white matter or subcortical structures. As a result the dosage reaching particular brain structures depends on a variety of factors such as cranium thickness, degree of cortical atrophy, penetrance, source of light, and duration of treatment/energy density of light.

9. Study Time Line Schedule of Activities

The Schedule of Participant Activities for this study is as follows:

- **Call #1**- Telephone Prescreening to review the study details, and inclusion/exclusions.
- **Informed Consent Process and Screening Visit**- Informed Consent Process begins with the participant per UF, state and federal guidelines. Once the participant has signed the informed consent, complete medical history, inclusion/exclusion criteria, concomitant medications, and cognitive and mood questionnaires will be administered (listed in section C). If participant formally meets study criteria, then he or she is invited to participate in the intervention phase of the study consisting of baseline, NIR stimulation, and post-baseline testing.
- **Baseline Visit** - This assessment involves a series of computer based measures and other questionnaires. This visit may take approximately 3-3.5 hours. If participants undergo MRI, this will take an additional 1.5 hours.
- **NIR Invention (six in lab sessions over two weeks)** - After completing baseline testing, participants will undergo a series of six interventions in the lab over a period of two weeks. The six treatment visits will be scheduled at the baseline visit to ensure availability of the participant. The treatment will be applied over the head and is detailed in section C. During each treatment visit, participants will fill out mood questionnaires such the POMS. .
- **Post-Treatment Visit**- Following the final day of stimulation, the participant will be scheduled for a post-testing assessment of cognitive and emotional function identical to the baseline visit. Participants will also fill out other questionnaires such as the adverse events and placebo control questionnaires.

10. Data Safety Monitoring Plan

The PI, Co-Is, or project coordinator will meet with each participant to review the adverse events questionnaires and assess for negative effects on the safety of participants. This questionnaire will be reviewed after every intervention session and at the follow up evaluation. As this intervention involves an infrared lamp that has been FDA approved as a non-significant risk, we do not anticipate adverse events or side effects. However, should a participant experience any adverse event of sufficient concern at any point during the intervention or at follow up, we will report to the IRB as directed. The PI and/or project coordinator will send via email a monthly report to the investigative team indicating the nature of any adverse events. If there are no reported adverse events, then an email summary will not be sent that month. The PI will take primary responsibility of the Data Safety and Monitoring Plan.

11. Data Management Plan

Data will be kept in a password protected encrypted database which can only be accessed by the investigator and her staff. All surveys and assessments will be under the direction of the Principal and 3.nvestigators who will supervise Research Assistants. Recruitment, screening, and project implementation will be coordinated by the co-investigator and/or research assistants. The existing data management group, supported by the IT department of the College of Public Health and Health Professions, will manage the database, monitor subject recruitment and distribute monthly enrollment reports, and produce reports summarizing the status of data acquisition, the baseline characteristics and the blinded primary variables.

The password protected encrypted database mentioned above is the storage place for all participants who call and wish to be pre-screened for the study. In many instances, the

prospective participant no longer wants to enroll in the study, once they learn of the time commitment and details involved in participating. At this point, they often ask if they could be contacted for other studies in the future. We will keep a column noting verbal consent to call in the future for short term, easier studies to participate in. If participants do not wish to be contacted in the future for other studies, that will be noted as well. This information will only be used by [name] laboratory for future research.

12. Possible Discomforts and Risks

The risks are minimal for individuals who participate in this study. Light is applied using light emitting diodes, which do not present as a serious ocular hazard. Near infrared light is non-thermal, painless, and was designated as a non-significant risk by the FDA in 2003. It is estimated that approximately 6 J/cm^2 is expected to reach the cortex with each daily treatment. At this energy level, the MedX MCT502 and Vielight 810 accessories do not cause tissue damage or physical damage.. As part of normal operation, the LED clusters may warm up during the application of light. The temperature of the MedX Clusters does not exceed 45° C (113° F) during operation.

There are four types of potential risks for participants in this study.

First, the completion of various screening and cognitive probes could potentially become boring or tiresome. To minimize fatigue associated with completion of screening and baseline tasks, participants will be given frequent breaks and the opportunity to rest.

Second, there is potential risk of loss of confidentiality. This will be minimized through assigning all data collection instruments a unique code without individual identifying information. All HIPAA regulations pertaining to protection of participants and eliminating identification will be followed.

Third, a subset of participants will undergo MRI. This is perhaps poses the greatest discomfort. Because the MRI scanner has a strong magnet, individuals with metal implanted in their body cannot participate. The scanner produces a loud hammering noise, which has produced hearing loss in a very small number of participants. All participants are provided with ear protection while in the scanner. There is not much room in the scanner and it can be uncomfortable to remain still for the scan. Individuals with known claustrophobia will be excluded from participating.

Fourth, it is also possible that incidental findings may emerge on the MRI. In this situation, the participant will be informed and recommendation/referrals will be made with the participant's permission. This could include provision of information to the participant's primary care physician and/or referral to another health care professional for followup.

For individuals with Parkinson disease, there is an additional potential discomfort. The PD participants may experience some increase in their symptoms (i.e., increased slowness, tremor, rigidity) when they are tested during the "off medication" state. This is similar to what occurs during their routine clinical evaluation at the Movement Disorders Clinic, when they are asked to come to their clinic appointment after being off their Parkinson medication overnight. For our research study, care will be taken to ensure that the Parkinson patients are transported by wheelchair when necessary and that they are accompanied by a member of the study team. They will be told that if they become too uncomfortable, then they should go ahead and take their medication.

It is possible that there are unknown risks for participating in this study. Individuals will be asked about side effects at each visit and encouraged to share information about subjective changes.

13. Possible Benefits

Cognitive and mood benefits cannot be guaranteed. However, it is possible that some participants may experience cognitive and mood benefits that may include improved memory, executive function, and mood. It is possible that individuals may experience some improvements solely due to expectations.

14. Conflict of Interest

No conflict of interest exists for the investigators of this protocol.

REFERENCES

- Barrett, D. W., & Gonzalez-Lima, F. (2013). Transcranial infrared laser stimulation produces beneficial cognitive and emotional effects in humans. *Neuroscience*, 230, 13–23. doi:10.1016/j.neuroscience.2012.11.016
- Beck, A. T., Steer, R. A., Ball, R., & Ranieri, W. (1996). Comparison of Beck Depression Inventories 1A and II in psychiatric outpatients. *Journal of Personality Assessment*, 67(3), 588–597.
- Chen, A. C. H., Huang, Y. Y., Arany, P. R., & Hamblin, M. R. (2009). *Role of reactive oxygen species in low-level light therapy*. Proceedings of the SPIE, 7165, Mechanisms for Low-Light Therapy IV, 716502. doi:10.1117/12.814890.

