6.6 Pre and Post-Intervention Measures

Participants who meet study criteria and who remain interested in participating in the 2 week intervention will be randomized to treatment or sham groups and undergo a baseline/ pre-intervention testing. The pre-intervention measures will be administered by a trained psychometrist or research assistant who will be blinded to group assignment (sham, real NIR stimulation).

The pre-intervention testing will take approximately 3 – 3.5 hours, and will consist of measures of executive function, recent memory, and mood. These same measures will be given after the two-week intervention has completed.

Individuals with Parkinson disease will complete the pre and post intervention visits when they are “off” their typical dopaminergic medications. This is identical to what Parkinson patients are asked to do as part of standard clinical care when seen at the UF Movement Disorders Clinic. To do so, the Parkinson patients will refrain from taking their parkinsonian medications overnight, with no dopa medication after 10:00 PM the night before. The theoretical rationale for evaluating patients when off dopamine medication is to obtain an index of the true status of their disease state.. The remainder of the protocol (i.e., screening, intervention) will be completed when participants are on their normal medications. When tested ‘off medication’, patients may experience increased slowness, tremors and stability. Because of this, they will be closely monitored and provided a wheel chair. If they become too uncomfortable they can take their medication and will be withdrawn from the study.

In previous IRB- approved studies, we have tested Parkinson patients off medication while they completed an array of cognitive, EEG, and other tasks. We have found that the tolerability was quite good and no participants dropped out of the study for the medication issue. In the current study, we are implementing testing ‘off dopa’ medications at the recommendation of the Parkinson Foundation.

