6.6.4b. Description of State Trait Anxiety Inventory (STAI; Spielberger, 1983a; 1983b; 1989). The STAI is a 40-item questionnaire that is used to assess current (state) and general (trait) levels of anxiety. Higher scores represent higher levels of anxiety, or feelings of worry, tensions, and stress. Items on the questionnaire include ratings of statements such as "I feel calm", "I am jittery", and "I feel nervous". The STAI has been used extensively in clinical and research settings and displays a test-retest reliability of 0.31 to 0.86 and internal consistency alpha coefficients of 0.86 to 0.95 (Spielberger et al., 1983a). Further, this measure shows high convergent validity with other measures of anxiety (0.72 to 0.86; Spielberger et al. 1989).

6.6.4c. Description of Profile of Mood States, short form (POMS, Curran et al., 1995). This is a 30 item self- report questionnaire of mood states such as "discouraged", "grouchy", "vigorous", and "efficient". The short form version of the POMS is easy to administer, and yields information about transient current mood states. The measure is grouped into subscales including tension, depression, anger, fatigue, and vigor. Test-retest reliability ranges from 0.65 to 0.74, internal consistency is 0.93, and the test also features high degrees of construct validity (Curran et al., 1995).

6.6.4d. Description of Beck Depression Inventory-II (BDI-II; Beck et al., 1996). This is a 21 item self-report questionnaire of symptoms of depression such as sadness, self-criticalness, loss of interest, or somatic changes such as insomnia or increased sleep, increased or decreased appetite, and low energy. This questionnaire allows one to characterize levels of depression as mild, moderate, or severe, depending on the total score. The BDI-II has strong convergent validity, internal consistency ($\alpha=.91$) and test-retest reliability ($r=.93$) and has been used extensively in clinical and psychological research.

6.6.4f. Description of Apathy Scale (AS, Marin et al., 1991). This is a 14 item self-report questionnaire that assesses for symptoms of motivation, drive, and initiative. Participants answer questions on a 5 point likert scale ranging from 0 to 4. The AS has been subgrouped into components reflecting cognitive, affective, and behavioral components of apathy. Test-retest reliability is strong, and the AS has strong convergent validity with real world indicators of behavior (Ferencz et al., 2012).

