6.7.3 Stimulation Session Procedure

In Lab Sessions: All participants will attend six NIR stimulation sessions. During each session, the participant will be seated comfortably in a chair. Clusters of LED's will be positioned across various regions of the scalp via a flexible nylon head cap that is appropriate to the participants head size. Onset of the NIR light stimulation will be controlled by the MEDX Console. Twenty minutes of stimulation will occur during each Set, for a total of 40 minutes NIR light application, with LEDs repositioned to a new position for each set. During the session, the 810 nm intranasal Vielight will be placed in each nostril and turned on once per session for 25 minutes (one dose) and subsequently removed.

During the actual stimulation period, participants will view nature documentaries (BBC Life documentary series; Gunton, 2009) that are shown on a monitor during the duration of stimulation. This is being done in order to standardize cognitive engagement and control for differences in cognitive activity during stimulation. This will also be done to reduce conversation between the examiners and the participant during the period of stimulation, which could differ between participants. Six episodes of the BBC Documentary will be presented in the same order for each participant, with a different episode played at each stimulation session. A brief description of each episode is provided below:

1. "Challenges of Life": This episode is the series opener and features stories of animal behavior such as feeding, hunting, and courting from around the world. Animals featured include killer whales, poison-dart frogs, and penguins.
2. "Mammals": This episode features the life of mammals from around the globe. Stories feature animals such as reindeer, polar bears, African elephants, and humpback whales.
3. "Birds": This episode features stories of birds from across the globe. Nesting, parenting, and migratory behaviors are described from animals such as humming birds, pelicans, grouses, and bowerbirds.
4. "Creatures of the Deep": This episode features an exploration of life in the deep ocean. Deep-sea creatures such as jellyfish, spider crabs, sea urchins, octopus, and coral reefs are described.
5. "Plants": This episode utilized time-lapse photography and videography to explore the behavior of plants. Featured plants include Venus flytraps, sundews, milkweeds, dragons blood trees and mangrove trees.

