6. "Primates": This episode features stories of primates and the attributes that have made them a highly successful group of mammals. Animals featured include lemurs, gibbons, orangutans, and macaques.

Other episodes include "Reptiles and Amphibians", "Fish", "Insects", and "Hunters and Hunted". These videos may be played if there is reason to need an extra video.

At Home Intranasal Sessions (optional). Each participant will be loaned an intranasal device, that is identical to the one used during the laboratory session. Participants will be asked to use the intranasal device for 25 minutes each day, except for days they visit the laboratory. The participants are trained to use the device during the initial lab visit and shown that the device

automatically cuts off after 25 minutes. Participants will be asked to keep a log of usage and to return the device at the completion of the study.

Equipment Sterilization

Following each session, the 6 MedX LED clusters and 2 Vielight intranasal leads will be sterilized with disinfectant wipes (PDI Super Sani-Cloth Germicidal Disposable Wipes) before storage. The manufacturer's recommendations are to clean equipment with sterilizing swabs in between sessions. In addition, a new flexible net caps will be used for each participant.

Questionnaires: Following the 40-minute stimulation period all participants will fill out the POMS short form and will be queried for adverse events (using the Adverse Events log). Completion of these questionnaires will take place at the end of each session.

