7.1. Outcome Measures

Aim 1 examines executive function and memory using sensitive cognitive measures.

- Co-Primary Executive Outcome: Changes in pre-post treatment scores on: a) executive composite and domain scores derived from the NIH Examiner and b) the Stroop interference score.

- Co-Primary Memory Outcomes: Changes in pre-post treatment scores on memory measures including a) delayed recall scores and composite from the Arena and b) delayed recall score from the AVLT. Secondary outcomes include other executive and memory measures as well as potential mediator and moderator variables such as processing speed.

Aim 2 examines well-being and mood variables.

- Co-Primary outcome: Changes in pre-post treatment scores on the Negative Affect and Psychological Wellbeing scales from the NIH Toolbox emotion module.
- Secondary outcomes: Changes in pre-post treatment scores on traditional mood measures including the 1) State-Trait Anxiety Inventory (STAI; Spielberg, 1989), the 2) Profile of Mood States (POMS; Curan et al., 1995), 3) Beck Depression Inventory-II (BDI-II; Beck et al., 1996), and 4) Apathy Scale.

Aim 3 is an exploratory neuroimaging aim that will examine changes in resting state functional connectivity as a function of group status (NIR stimulation vs Control). We are particularly interested in potential changes in MRS spectroscopy, particularly those elements associated with phosphorous ATP

Aim 4 pertains to motor variables that are being examined in patients with Parkinson disease

- Outcomes include: Changes in pre-post intervention scores on the Grooved Pegboard Task, scores on the UPDRS rating scale, and gait and balance measures on the GAIT-Rite scale.

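### Six of the seven post-baseline POMS scores have no planned analysis, and participants without a follow-up score drop out of the change-score test

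*Protocol*

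**What the plan says.** **Collection.** Protocol section 6.7.3 states "All participants will attend six NIR stimulation sessions" and, under Questionnaires, "Following the 40-minute stimulation period all participants will fill out the POMS short form and will be queried for adverse events". The section 6.7 overview and the section 9 schedule agree. Table 2 marks POMS at baseline, intervention and follow-up, and it is the only efficacy scale marked in the intervention column. Section 6.6 covers the repeat of the baseline battery: "These same measures will be given after the two-week intervention has completed".

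**Analysis.** Section 7.1 lists POMS among the Aim 2 secondary outcomes, defined as "Changes in pre-post treatment scores on traditional mood measures". Section 7.3 says that 2 (group) x 2 (pre, post) mixed ANOVAs "will be conducted using the mood outcome variables (mood modules NIH Toolbox, STAI, POMS, BDI-II", separately in each diagnostic group. The SAP replaces this with independent t-tests on post minus baseline, giving the small sample as the reason. With two occasions this is the same contrast as the group-by-occasion term. Neither document gives the session scores an analysis or says why they are collected.

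**Analysis set.** Section 7.2.b defines the intention-to-treat set as participants who took part in at least one week of the assigned intervention, whether or not they completed the study. Section 6.2 expects 20% attrition. No handling of a missing follow-up score is described.

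**The concern.** POMS is the one efficacy measure taken repeatedly during treatment, and the plan uses only its two ends. Three things are at stake.

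- **Lost participants.** Sessions run three a week, so someone who stops after week 1 belongs to the intention-to-treat set and has a baseline score and about three session scores. Without a follow-up score, a change-score t-test cannot include that person.
- **Time course.** Two points cannot show when a mood difference appears or whether it persists.
- **Precision.** The groups are small (35, 20 and 10 per arm), and section 6.7.2 says the protocol is kept brief because its purpose is to judge effect sizes and feasibility. An unadjusted change score is not the most precise use of the baseline.

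**Working it through.** **Counts.** 1 baseline + 6 sessions + 1 follow-up = 8 scores. Seven are post-baseline, one of those is analysed, and six are not.

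**Inputs.** Section 6.6.4c: "Test-retest reliability ranges from 0.65 to 0.74", with no retest interval. The documents give no POMS standard deviation, effect size or power, so there is no planned figure to reproduce. I take the retest range as the correlation r, with equal variances at all visits. Variances are per unit score variance; the common factor 2/n per arm cancels in ratios.

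**Formulas, with one common r for every pair of visits**

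- A. Follow-up minus baseline (the plan): 2(1 − r)
- B. Follow-up, baseline-adjusted: 1 − r²
- C. Mean of seven minus baseline: (8/7)(1 − r)
- D. Mean of seven, baseline-adjusted: (1 + 6r)/7 − r²

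| r | A | B | C | D | A/B | A/C | A/D | B/D |
|---|---|---|---|---|---|---|---|---|
| 0.65 | 0.700 | 0.578 | 0.400 | 0.278 | 1.21 | 1.75 | 2.52 | 2.08 |
| 0.70 | 0.600 | 0.510 | 0.343 | 0.253 | 1.18 | 1.75 | 2.37 | 2.02 |
| 0.74 | 0.520 | 0.452 | 0.297 | 0.230 | 1.15 | 1.75 | 2.27 | 1.97 |

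A simulation at r = 0.70 with 35 per arm gave A/C = 1.75 and A/D = 2.33. The small shortfall from 2.37 is the cost of estimating the baseline slope, a factor of 1 + 1/(2n − 4) = 1 + 1/66 = 1.015. With 10 per arm that factor is 1 + 1/16 = 1.0625, so A/B in each MCI group falls to about 1.15/1.0625 = 1.08 up to 1.21/1.0625 = 1.14.

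**Same estimand as the plan.** Only A/B compares two estimates of the follow-up effect. With free treatment-by-visit means and complete data, the mixed model gains essentially nothing from the session scores at follow-up, so the 1.15 to 1.21 comes from baseline adjustment alone.

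**Sensitivity of the time-averaged ratios.** If post-baseline scores correlate at 0.80 with each other and at r with baseline, the variance of the seven-score mean is (1 + 6 × 0.80)/7 = 0.829.

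- A/C: 0.70/(1.829 − 1.30) = 1.32 at r = 0.65, and 0.52/(1.829 − 1.48) = 1.49 at r = 0.74.
- A/D: 0.70/(0.829 − 0.4225) = 1.72, and 0.52/(0.829 − 0.5476) = 1.85.

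Under serial decay over assumed visit days 0, 1, 3, 5, 8, 10, 12 and 15, A/C is 2.3 to 2.9 and A/D is 2.7 to 3.3.

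**If the effect builds up.** With a linear rise over the seven occasions, the mean carries (1 + 2 + … + 7)/49 = 28/49 = 57% of the final effect. Squared signal-to-noise relative to the plan is 0.571² × A/D = 0.327 × 2.27 to 0.327 × 2.52 = 0.74 to 0.82 with baseline adjustment, and 0.327 × 1.75 = 0.57 without. The adjusted mean breaks even only if the averaged effect is at least 1/√2.52 = 63% to 1/√2.27 = 66% of the final one.

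**The case against.** The case for leaving the session scores out deserves weight.

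- **A different effect.** The plan targets change from before to after treatment. The seven-score mean targets average mood from the first session onward and, as shown, can be less powerful if benefit accrues gradually. This stands, and it is why the averaged effect should not replace the follow-up contrast.
- **Different conditions.** Session forms are completed straight after 40 minutes of stimulation and film, on a scale that section 6.6.4c describes as measuring transient mood. Under section 6.6, Parkinson participants are on dopaminergic medication at sessions and off it at baseline and follow-up. Both arms share this and groups are analysed separately, so the randomised comparison at each visit is intact. Averaging mixes the two states, however, and strains the common-correlation assumption for 40 of the 150 planned participants.
- **Missing follow-up may be limited.** Section 7.2.b encourages people who stop treatment to attend post-testing. That reduces the loss but does not say what happens when they do not attend.
- **Small groups.** With 10 per arm, seven responses and an unstructured covariance would be fragile. A simple structure is needed there.
- **Timing.** The SAP is written in the past tense, so a change now may be post hoc.

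A reader might infer that ignoring six scores more than doubles the variance of the planned treatment effect, or that using them is like having 2.3 to 2.5 times as many participants. The documents support neither. Under the plan's own change-score method the ratio is 1.75. The larger figures also require a switch to baseline adjustment and a correlation structure that the documents do not give. All of these ratios refer to a time-averaged effect, and the sample-size reading holds only if the effect is fully present from the first session.

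**Conclusion.** The gap is real and its size is modest. Both documents confine POMS to a pre-post contrast although eight scores are scheduled, and neither says what the other six are for. The firm losses are participants without a follow-up score, the time course, and a 1.15- to 1.21-fold variance for the follow-up contrast (about 1.08 to 1.14 in the MCI groups). That last figure rests on equal variances and on reading the stated retest range as the baseline-to-follow-up correlation. The gain from retaining incomplete participants cannot be quantified, because the documents do not say how many would lack follow-up, and it relies on data being missing at random. The time-averaged ratios depend on an assumed correlation structure and should be quoted as a range. POMS is one of four secondary Aim 2 measures in a pilot, so no co-primary conclusion is affected. The change is worth making because it is cheap.

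**What to change.** State in the SAP what the session POMS scores are for, and analyse POMS within each diagnostic group with a linear mixed model:

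- baseline score as covariate; sessions 1–6 and follow-up as repeated responses; treatment, visit and treatment x visit as fixed effects;
- a named covariance structure, kept simple in the two MCI groups;
- every randomised participant with any post-baseline score included, with the missing-at-random assumption stated;
- the treatment difference at follow-up as the main POMS result;
- visit-specific and averaged during-treatment differences as supporting results, with a note that session forms follow directly after stimulation and, in the Parkinson group, a caveat about medication state.

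If outcome data have already been examined, keep the planned t-test in the report and label the model post hoc. The cost is a paragraph of SAP text and one model per group; no new data are needed. The drawbacks are the extra modelling assumptions in small groups and the need to keep the averaged effect from being read as the post-treatment effect.
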